8.7 Selection of giving set tubing SKUs

During **eligibility screening**, patient e-medical records will be reviewed to allow operators to determine if the Mobility+ system is suitable for potential participants based on the enteral nutrition formula the person uses, their **estimated** flow rate needs (mls/hour), and the information in the Mobility+ Flow Rate Guide (FRG) on indicative flow rates achieved with various formula and tubing SKU combinations. *Note: The process of healthcare professionals using the FRG to allow selection of an appropriate tubing SKU is validated by expert review.*

Operators will use FRG and the potential participant's enteral feeding regimen prescription to estimate which giving –set tubing SKU (from four available options) best suits the participant's needs, with the approach being to pick the SKU which will provide a flow rate that is slightly slower than the participant's estimated flow rate. The operator will refer to the Decision Tree for Prescribing Mobility+ (see **Figure 6**) when deciding if the potential participant should be invited for a clinic visit.

- Decision Tree Questions
- Giving Set SKU suitable for patient
- No Giving Set SKU suitable for patient

Figure 6: Decision Tree for prescribing Mobility+

During the clinic visit, the operator will administer the screening questionnaire (**Appendix 2**) which will allow the operator to gauge the participant's **calculated average flow rate**. The operator will then use the participant's calculated average flow rate, the FRG and Decision Tree for Prescribing Mobility+ (see **Figure 6**) to make a final decision on which giving set SKU the participant will begin the trial period with. As per the Decision Tree for Prescribing Mobility+, the operator will prescribe the giving set SKU which provides a flow rate slower than the participant's calculated average flow rate and exercise caution when prescribing the 1900mm for use in the trial. This reduces the likelihood of the participant starting the trial with flow rates that are too high, and reduces the risks associated with this e.g. nausea and vomiting, among others. The trial period will allow time for an assessment on whether this initially selected tubing SKU is the best-fit for the participant to continue to use for the study days.

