8.10 Clinic Visit

The following activities are carried out during the clinic visit.:

- Provide the information sheet to the participant. Obtain informed consent verbally and via e-signature, and agreement with data privacy policy[sw1].
- Officially enroll participant.
- Administer the screening questionnaire (**Appendix 2**) to confirm participant eligibility
- Revisit the FRG and Decision Tree for Prescribing Mobility+, and use the additional information generated through the screening questionnaire to make a final decision on the appropriate giving-set tubing SKU (**Appendix 2**) for participants to begin the trial period with.
- Advise participant that operators (licensed to prescribe) may change the giving-set tubing SKU participants are to use, during the trial and or study days, if clinical and participant factors indicate this is needed (e.g. participant reflux may necessitate a change to slower flow rate, or participant finding feeding times too long may necessitate a change to a faster flow rate)
- Answer any queries
- Record the demographic data including calorie intake (**Appendix 3**).

	
Safety and Effectiveness of A Novel Enteral Feeding System: Prospective Study Protocol Page 23 of 49
	
NCT06173063

---	---	--

- Administer the participant perspectives baseline survey (**Appendix 4**) and quality of life survey (**Appendix 5**).
- Provide familiarization training as per **Appendix 11**.
- Provide necessary consumables.

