Which type of feeding tube do you have?	G-tube 	J-tube 

Appendix 4
Participant perspectives baseline survey

 Participant perspectives of current feeding system: Usability, mobility and ease of use

(Operator asks the Participant these questions)

During use of your current feeding system, how do you find these activities?	Very Difficult	Difficult	Neutral	Easy	Very Easy	
Moving from one room to another room						
Going up and down stairs						
Short walk (e.g., one block)						
Long walk (e.g., several blocks)						
Travelling in car/public transport						
Moderate intensity physical activities, such as: - Moving a table - Pushing a vacuum - Bowling - Playing golf						
Other daily activities (e.g., lifting or carrying groceries, household chores)						
Ability to sleep						
Socializing with friends/family						
During use of your current feeding system, how do you find working/studying or both? Please log as N/A if participant does neither.	Very Difficult	Difficult	Neutral	Easy	Very Easy	N/A
Note to operator: When scoring this questionnaire, assign points using the legend below. Very Difficult = 0 points, Somewhat Difficult = 1, Neutral = 2, Somewhat Easy = 3 and Very Easy = 4						
Thinking about your overall experience with your current system, how strongly do you	Strongly Disagree	Some-what Disagree	Neutral	Some-what Agree	Strongly Agree	

agree or disagree with the following statements?					
My current system is easy to use					
My current system is easy to carry					
The noise level of my current system during use (including alarms) is acceptable					
My current system allows me to feed discreetly					
I am satisfied with the overall performance of my current system					
Note to operator: When scoring this questionnaire, assign points using the legend below. Strongly Disagree = 0 points, Somewhat Disagree = 1, Neutral = 2, Somewhat Agree = 3 and Strongly Agree = 4					
Do you experience any of the following symptoms of feed intolerance while using your current feeding system?					
Gas/Bloating?	 Yes			 No	
If yes, is it mild, moderate, or severe?	 Mild	 Moderate	 Severe		
Abdominal Pain?	 Yes			 No	

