If yes, is it mild, moderate, or severe?	 Mild	 Moderate	 Severe		
Diarrhea?	 Yes			 No	
If yes, is it mild, moderate, or severe?	 Mild	 Moderate	 Severe		
Constipation?	 Yes			 No	
If yes, is it mild, moderate, or severe?	 Mild	 Moderate	 Severe		
Nausea/Vomiting?	 Yes			 No	
If yes, is it mild, moderate, or severe?	 Mild	 Mild	 Mild		
Reflux?	 Yes			 No	
If yes, is it mild, moderate, or severe?	 Mild	 Mild	 Mild		

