experience with the Mobility+ system, how strongly do you agree or disagree with the following statements?	Strongly Disagree	Some-what Disagree	Neutral	Some-what Agree	Strongly Agree
The Mobility+ system is easy to use					
The Mobility+ system is easy to carry					
The silent nature of The Mobility+ system during use is acceptable					
The Mobility+ allows me to feed discreetly					
I am satisfied with the overall performance of the Mobility+ system					
Note to operator: When scoring this questionnaire, assign points using the legend below. Strongly Disagree = 0 points, Somewhat Disagree = 1, Neutral = 2, Somewhat Agree = 3 and Strongly Agree = 4					
Do you experience any of the following symptoms of feed intolerance while on your current feeding system?					
Gas/Bloating?	□ Yes			□ No	
If yes, is it mild, moderate, or severe?	Mild □	Moderate □	Severe □		
Abdominal Pain?	□ Yes			□ No	
If yes, is it mild, moderate, or severe?	Mild □	Moderate □	Severe □		
Diarrhea?	□ Yes			□ No	
If yes, is it mild, moderate, or severe?	Mild □	Moderate □	Severe □		
Constipation?	□ Yes			□ No	
If yes, is it mild, moderate, or severe?	Mild □	Moderate □	Severe □		
Nausea/Vomiting?	□ Yes			□ No	
If yes, is it mild, moderate, or severe?	Mild □	Moderate □	Severe □		
Reflux?	□ Yes			□ No	
If yes, is it mild, moderate, or severe?	Mild □	Moderate □	Severe □		
Have you been admitted to hospital since you last received phone communication?	□ Yes			□ No	
General End of Study Questions:					

When answering the following questions, consider how **the last 14 days with Mobility+** have been compared to an average week of using the feeding system that you had **before you started this study**. Please try to answer based **solely on your experience with the Mobility+** in the last two weeks and not on external factors that may have positively/negatively impacted your week of using the Mobility+.

How do you feel your overall Quality of Life has been during the last 2 weeks of using Mobility+?

Excellent	Good	Neutral	Bad	Very Bad
				

How mobile have you been in your everyday activities during the last 2 weeks of using Mobility+, compared to before you started the study?

Much Better	Somewhat Better	About the Same	Somewhat Worse	Much Worse
				

How do you rate the importance of being mobile in your everyday activities to your overall wellbeing?

Very Important	Somewhat important	Not important at all

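### Two baseline symptom-severity items, nausea/vomiting and reflux, offer only a mild grade as printed and so are not comparable with the Day 14 form

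*Protocol*

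**What the plan says.** Protocol 3.0 makes tolerance, with the usual system and with Mobility+, part of a secondary endpoint measured by the surveys in Appendices 4 (baseline) and 7 (end of study). Both forms list six symptoms, each with a yes/no answer and then a severity question, "If yes, is it mild, moderate, or severe".

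The answer boxes differ:

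- Appendix 4, gas/bloating, abdominal pain, diarrhea, constipation: "Mild Moderate Severe".
- Appendix 4, nausea/vomiting and reflux: "Mild Mild Mild".
- Appendix 7, all six symptoms: "Mild □ Moderate □ Severe".

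Both forms are administered by an operator ("Operator asks the Participant these questions"). Protocol 11.1 has the answers entered straight into REDCap; the field labels there are not shown.

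The protocol links both affected symptoms to flow rate. Section 8.7 says that starting slower than the participant's calculated average rate "reduces the risks associated with this e.g. nausea and vomiting, among others". Section 8.10 gives as an example that "participant reflux may necessitate a change to slower flow rate".

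No severity analysis is defined. Table 5 (Protocol 11.2) scores only the Likert items. SAP 4.0 scores mobility, ease of use and quality of life. The test in SAP 5.0 is not tied to symptoms.

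**The concern.** The study has a single arm, so each participant's own baseline is the only comparator for tolerance. A baseline item that can record a symptom only as absent or mild, set against a Day 14 item with three grades, cannot support a severity comparison. Someone with severe reflux at both visits would appear to go from mild to severe, and someone who improved from severe to mild would appear unchanged.

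SAP 7.0 reports outcome data for 17 participants, so a few misgraded baselines could change the look of a severity table. Severity is collected at both visits for a named endpoint, and no written rule stops someone from tabulating the change.

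**Working it through.** The documents give no figure on symptom severity, so there is none to reproduce. The check compares the two forms and then works out what the printed labels would do.

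**Extent.** 2 of 6 baseline severity items are affected (2/6 = 33%). This counts items on the form; it is not an effect size.

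**Severity pairs.** Code mild = 1, moderate = 2, severe = 3 (a coding chosen for this check). Take participants with the symptom at both visits and suppose that every baseline answer was recorded as mild. Recorded change is then the Day 14 grade minus 1.

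| True baseline → Day 14 | True change | Recorded change |
|---|---|---|
| mild → mild | 0 | 0 |
| mild → moderate | +1 | +1 |
| mild → severe | +2 | +2 |
| moderate → mild | −1 | 0 |
| moderate → moderate | 0 | +1 |
| moderate → severe | +1 | +2 |
| severe → mild | −2 | 0 |
| severe → moderate | −1 | +1 |
| severe → severe | 0 | +2 |

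True split: 3 worse, 3 better, 3 unchanged. Recorded split: 6 worse, 0 better, 3 unchanged. One true improvement (severe to moderate) is recorded as worsening. The largest error is 2 grades. With correct labels the recorded split equals the true one.

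**Apparent mean shift when nothing truly changes.** Let p_mod and p_sev be the shares of symptomatic participants who are moderate or severe at baseline, and f the share of those answers recorded as mild. Then

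apparent shift = f × (p_mod + 2 × p_sev).

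The documents give none of these three quantities, so all values below are assumptions.

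| p_mod | p_sev | f = 1 | f = 0.5 | f = 0 |
|---|---|---|---|---|
| 0.20 | 0.05 | 0.20 + 0.10 = +0.30 | +0.15 | 0 |
| 0.40 | 0.10 | 0.40 + 0.20 = +0.60 | +0.30 | 0 |
| 0.40 | 0.20 | 0.40 + 0.40 = +0.80 | +0.40 | 0 |
| 0.50 | 0.30 | 0.50 + 0.60 = +1.10 | +0.55 | 0 |

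**Other ways the form may have been used.** If the operator ticked by box position, or the REDCap choices were correct, f = 0 and nothing is lost. If moderate and severe answers were left blank, the remaining mild grades are right, but everyone who was moderate or severe drops out of the comparison. If those participants stayed stable while some mild ones worsened, the remaining data overstate mean worsening. If they worsened while the mild ones stayed stable, the remaining data understate it. The direction is therefore not fixed.

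**The case against.** A reader might infer that severity change in these two symptoms is biased toward worsening, full stop, and that the severity part of the tolerance endpoint is wrong. The documents do not support either statement. The question on the same rows still names three grades, there are still three boxes, an operator reads the question aloud, and the REDCap labels are unknown. Bias, missing data and no effect all remain possible. No severity-change measure is planned in the Protocol or SAP, and none is reported, so there is no result to call wrong.

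It can also be said that the repeated label may come from the reading of the PDF. That cannot be excluded, but the same repeat in two adjacent rows, with the other four severity rows of the form intact, makes a form error more likely. The source form will settle it.

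Calling these the two symptoms most relevant to the device would also go too far. The text in 8.7 and 8.10 names them as examples, and the Day 7 reasons for changing tubing in Appendix 8 include abdominal discomfort, which is closer to an unaffected item.

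Finally, the number of the 17 participants with moderate or severe nausea/vomiting or reflux at baseline is not given and may be zero. If the printed labels were followed, the distortion runs against Mobility+ and would not produce a falsely favourable claim.

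All of this limits the size and certainty of the point. It does not remove the mismatch between the two forms, and Appendix 14 lists the Appendix 4 survey for expert review as validation, so its answer options should be right.

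**Conclusion.** The point holds in conditional form. As printed, the baseline severity items for nausea/vomiting and reflux contradict their own question and do not match Day 14.

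If the labels were followed, severity change among those symptomatic at both visits can only be none or worse. The apparent shift with no true change would be +0.30 to +1.10 points on a 1 to 3 scale under the severity mixes assumed above, and half that if half of the moderate and severe answers were misrecorded. If the electronic form was right or box position was used, the effect is zero. If answers were left blank, data are missing and the bias has no fixed direction.

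The yes/no record of each symptom is unaffected, and so is the primary endpoint. The conclusion rests on the form text being as shown, which still has to be checked. The other four symptoms should not be taken as sound by default: the Day 14 symptom question in Appendix 7 refers to the participant's present system and does not name Mobility+. That is a separate ambiguity across all six symptoms.

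**What to change.** 1. Check the source Appendix 4 form, the REDCap field choices, and how operators recorded the baseline answers for these two symptoms.
2. Correct the form, and REDCap where needed, to mild, moderate and severe. SAP 6.0 and 7.0 show that the data were already gathered, so this helps only future use; the data in hand depend on steps 1 and 3.
3. If baseline was captured with the printed options, or this cannot be established, report nausea/vomiting and reflux as present or absent only, at baseline and at Day 14, and say so in the SAP and the study report.
4. If the check shows that all three grades were captured correctly, state that, and this obstacle to a severity comparison is removed.

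The cost is a lookup, a form correction and one line of text. The downside of step 3 is the loss of a severity comparison for two symptoms, which would not have been interpretable in that case.

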Appendix 5**QoL survey**

(Operator asks the Participant these questions)

Reference: Elfadil OM, Patel A, Abdelmagid M, et al. 1117929 - Mental Health Among Enteral Feeding Patients and Caregivers: Is Home Enteral Nutrition Overwhelming? Nutrition and Metabolism Research Oral Paper Session Abstracts. ASPEN Nutrition Science & Practice Conference: March 26-29, 2022 (Seattle, WA). JPEN J Parenter Enteral Nutr. 2022 Mar;46 (S1) <https://aspenjournals.onlinelibrary.wiley.com/doi/full/10.1002/jpen.2344>

Rate your quality of life	Excellent	Good	Neutral	Bad	Very Bad

Appendix 6
Phone Communication check sheet – Trial days

(Operator to use this check sheet to log tubing SKU and changes)

Tubing SKU check								
Trial Day 1: SKU that participant is using: 
 
 440mm RED 	700mm BLUE 	1000mm GREEN 	1900mm WHITE 	
 
					440mm RED 	700mm BLUE 	1000mm GREEN 	1900mm WHITE 
440mm RED 	700mm BLUE 	1000mm GREEN 	1900mm WHITE 					
Select one: 		Stay on this SKU 						
		Trial _____ SKU 						
Reason for changing: <hr/>								
Trial Day 3: SKU that participant is using: 
 
 440mm RED 	700mm BLUE 	1000mm GREEN 	1900mm WHITE 	
 
					440mm RED 	700mm BLUE 	1000mm GREEN 	1900mm WHITE 
440mm RED 	700mm BLUE 	1000mm GREEN 	1900mm WHITE 					
Select one: 		Stay on this SKU 						
		Trial _____ SKU 						
Reason for changing: <hr/>								
Trial Day 5: SKU that participant is using: 
 
 440mm RED 	700mm BLUE 	1000mm GREEN 	1900mm WHITE 	
 
					440mm RED 	700mm BLUE 	1000mm GREEN 	1900mm WHITE 
440mm RED 	700mm BLUE 	1000mm GREEN 	1900mm WHITE 					
Select one: 		Stay on this SKU 						
		Trial _____ SKU 						
Reason for changing: <hr/>								
Have you been admitted to hospital in the last 5 days/during this trial period?		 Yes		 No				
Note to operator: Confirm you have reminded participant of the day they will begin the 14 day study period		 Yes		 No				

Appendix 7

Participant perspectives outcome survey

Participant perspectives of Mobility+ feeding system: Usability, mobility, and ease of use, including general end of study questions

(Operator asks the Participant these questions)

During use of the Mobility+ system, how do you find these activities?		Very Difficult	Difficult	Neutral	Easy	Very Easy
Moving from one room to another room						
Going up and down stairs						
Short walk (e.g., one block)						
Long walk (e.g., several blocks)						
Travelling in car/public transport						
Moderate intensity physical activities, such as:						

 - Moving a table - Pushing a vacuum - Bowling - Playing golf 						
Other daily activities (e.g., lifting or carrying groceries, household chores)						
Ability to sleep						
Socializing with friends/family						
During use of the Mobility+ system, how did you find working/studying or both? Please log N/A if participant does neither	Very Difficult	Difficult	Neutral	Easy	Very Easy	N/A
Note to operator: When scoring this questionnaire, assign points using the legend below.						
Very Difficult = 0 points, Somewhat Difficult = 1, Neutral = 2, Somewhat Easy = 3 and Very Easy = 4						
Thinking about your overall						

experience with the Mobility+ system, how strongly do you agree or disagree with the following statements?	Strongly Disagree	Some-what Disagree	Neutral	Some-what Agree	Strongly Agree
The Mobility+ system is easy to use					
The Mobility+ system is easy to carry					
The silent nature of The Mobility+ system during use is acceptable					
The Mobility+ allows me to feed discreetly					
I am satisfied with the overall performance of the Mobility+ system					
Note to operator: When scoring this questionnaire, assign points using the legend below. Strongly Disagree = 0 points, Somewhat Disagree = 1, Neutral = 2, Somewhat Agree = 3 and Strongly Agree = 4					
Do you experience any of the following symptoms of feed intolerance while on your current feeding system?					
Gas/Bloating?	□ Yes			□ No	
If yes, is it mild, moderate, or severe?	Mild □	Moderate □	Severe □		
Abdominal Pain?	□ Yes			□ No	
If yes, is it mild, moderate, or severe?	Mild □	Moderate □	Severe □		
Diarrhea?	□ Yes			□ No	
If yes, is it mild, moderate, or severe?	Mild □	Moderate □	Severe □		
Constipation?	□ Yes			□ No	
If yes, is it mild, moderate, or severe?	Mild □	Moderate □	Severe □		
Nausea/Vomiting?	□ Yes			□ No	
If yes, is it mild, moderate, or severe?	Mild □	Moderate □	Severe □		
Reflux?	□ Yes			□ No	
If yes, is it mild, moderate, or severe?	Mild □	Moderate □	Severe □		
Have you been admitted to hospital since you last received phone communication?	□ Yes			□ No	
General End of Study Questions:					

When answering the following questions, consider how **the last 14 days with Mobility+** have been compared to an average week of using the feeding system that you had **before you started this study**. Please try to answer based **solely on your experience with the Mobility+** in the last two weeks and not on external factors that may have positively/negatively impacted your week of using the Mobility+.

How do you feel your overall Quality of Life has been during the last 2 weeks of using Mobility+?

Excellent	Good	Neutral	Bad	Very Bad
				

How mobile have you been in your everyday activities during the last 2 weeks of using Mobility+, compared to before you started the study?

Much Better	Somewhat Better	About the Same	Somewhat Worse	Much Worse
				

How do you rate the importance of being mobile in your everyday activities to your overall wellbeing?

Very Important	Somewhat important	Not important at all
		

How strongly do you agree with the following statement? I would like to use the Mobility+ again.

Strongly Agree	Somewhat Agree	Neutral	Somewhat Disagree	Strongly Disagree
				

If you would like to use Mobility+ again, how often would you like to use it?

Every Day	Every Week	Every Month
		

Think about your overall wellbeing if you used Mobility+ for SOME/ALL of your tube feeding needs, in the long term. How would your wellbeing be then, compared to now?

Much Better	Somewhat Better	About the Same	Somewhat Worse	Much Worse
				

Would you pay out of pocket for the Mobility+?

YES	NO
	

How did you choose to wear the Mobility+ system?

- Crossbody bag**
- Handbag**
- Backpack**
- In clothing**
- Clipped onto belt/clothing**
- Other (Detail):**

Appendix 8

Appendix 8 - Phone communication check sheet (Study Day 7 and 14) - (Operator asks the Participant these questions)

Day 7

Day 7			
Questions:	Answers:		
Day 7 Safety & Effectiveness Check			
Are you able to use Mobility+ to successfully and safely provide enteral feeding?	 YES  NO		
Day 7 Compliance & Calorie Intake Check			
Consider your feed intake over the last 3 days (i.e. Study day 4, 5, 6).			
Questions:	Answers:		
What volume of enteral nutrition did you consume on average per day (i.e. over 24 hr)?	Volume Mobility+mls		
How many hours did you typically infuse for, on average/day? hours minutes		
How many feedings did you intend to take using Mobility+ , on average / day?feedings		
How many feedings were you able to take using Mobility+ , on average / day?feedings		
What was the average volume of enteral nutrition that you consumed per feeding with Mobility+?mls		
What time of the day did you provide feedings with Mobility+?	Morning  Afternoon  Evening  Night-time 		
Operator facing question: On average, did the participant take at least two daily feeds with Mobility+? If no, why not?	 YES		
	 NO		
Day 7 Tubing SKU check			
Study Day 7:			
SKU that participant is using:			
440mm RED 	700mm BLUE 	1000mm GREEN 	1900mm WHITE 

Select one:	Stay on this SKU 	Trial  SKU 
Reason for changing:	
Intolerance  Taking too long to feed  Abdominal discomfort  Unable to tolerate feed 
	

Day 14

Day 14 Tubing SKU Check			
What giving set tubing are you using?			
440mm RED 	700mm BLUE 	1000mm GREEN 	1900mm WHITE 
Day 14 Safety & Effectiveness Check			
Are you able to use Mobility+ to successfully and safely provide enteral feeding?	YES 	NO 	
Day 14 Compliance & Calorie Intake Check			
Consider your feed intake over the last 3 days (i.e., Study Day 11, 12, 13).			
What volume of enteral nutrition did you consume on average per day (i.e. over 24 hr)	Volumemls	Volume Other Systemmls	
How many hours did you typically infuse for, on average/day? hours minutes	
How many feedings did you intend to take using Mobility+, on average / day? feedings		
How many feedings were you able to take using Mobility+, on average / day? feedings		
What was the average volume of enteral nutrition that you consumed per feeding with Mobility+?mls		
What time of the day did you provide feedings with Mobility+?	 Morning  Afternoon  Evening  Night-time		

Safety and Effectiveness of A Novel Enteral Feeding System:
Prospective Study Protocol
Page 41 of 49

NCT06173063

Operator facing question:	On average, did the participant take at least two daily feeds with Mobility+?	YES 	NO 
	If no, why not?	

Appendix 9

Adverse event classifications

The below figures from ISO 14155:2020 highlight the process to be followed to determine if an AE or device deficiency is one of the below:

- AE
- SAE
- ADE
- SADE
- ASADE
- USADE
- Device deficiency with SADE potential
- Device deficiency without SADE potential

Table F.1 — Categories of adverse events

Adverse events	Non-device-related	Device- or investigational procedure-related	
Non-serious	Adverse event (AE) ^a (3.2)	Adverse device effect (ADE) ^c (3.1)	
Serious	Serious adverse event (SAE) ^b (3.45)	Serious adverse device effect (SADE) (3.44)	
		Anticipated	Unanticipated
		Anticipated serious adverse device effect (ASADE) ^c (3.1, Note 1 to entry)	Unanticipated serious adverse device effect (USADE) (3.51)

^a Includes all categories.
^b Includes all categories that are serious.
^c Includes all categories that are related to the device or the investigational procedure.

[figure not shown]

Figure F.1 — Adverse events categorization chart

The flowchart below on device deficiencies should only be used in case the device deficiency is not associated with an adverse event.

[figure not shown]

Figure F.2 — Device deficiency categorization chart

Appendix 10
Adverse Events Logging Method

The PI undertakes to report serious matters in a timely manner (within 24 hours) to the sponsor including details on the below:

- Participant ID
- Operator ID
- Incident date and time
- Incident details Incident category
- PI assessment details
- Determination
- Action
- Time PI reported assessment to Sponsor

Appendix 11

Participant Familiarization Training

This familiarization training matches typical training provided for new users of new enteral feeding systems on discharge and consists of a 1:1 demonstration of the system, including bringing attention to the labelling of the system, to minimize the potential for user errors to occur during unsupervised home use. Participants will attend a short 1:1 training session with a trained operator where they will be trained on Filling Method A (Filling from feed poured into a container), flushing, feeding, and wearing, as below. The setting will be a room in a clinical environment.

- Provide participant with Instructions for Use (IFU) booklet, a Mobility+ feeding pouch, giving set tubing, filling-set tubing, an ENFIT syringe and a cross-body bag
- Inform participant of the option to consult an instructional video, which can be accessed via smart device by scanning QR code on the IFU

Filling

- Demonstrate **Filling Method A** steps by filling a pouch with some water or formula.

Feeding

- Demonstrate 'feeding' by letting the Feeding Pouch (with giving-set attached) deliver some of its contents into a beaker.
- Explain the Feeding pouch deflates and reduces in weight as liquid feed is delivered, and the feed session is finished when no more liquid flows out of the tubing
- Advise the participant they can hold their Feeding pouch at times during feeding, to get used to feeling the pouch deflating and reducing in weight

Flushing

- Take the participant through the flushing section of the IFU

Wearing

- Show the participant the IFU guidance on how to loosely coil the giving set tubing and advise them to place the giving set tubing in the bag/clothing they choose to wear the system in (without kinking the tubing).

Hazards

- Ensure the participant is aware of the warning statement and precautions in the IFU

Notes:

- Extension set tubing may be left outside any bag/clothing the device is being worn in
- The Feeding Pouch is not to be squeezed during set up or use. The only time it is appropriate to squeeze the pouch is during flushing

Appendix 12
Participant familiarization training record

Date.....

Participant ID/.....

Operator ID.....

Familiarization training was conducted and the participant was taken through filling (filling method A), feeding, flushing, and wearing, as per the Instructions for Use, and given opportunity to execute the steps necessary for them to use the Mobility+ system at home to obtain their necessary nutrition.

Participant Signature

Operator signature

Appendix 13
Operator training record

Date.....
Operator ID.....

Operator self- training on use of Mobility+ device was conducted.

Operator was trained in execution of this study protocol (CLP001) by the sponsor Rockfield Medical Devices.

Operator signature

Sponsor signature

Appendix 14

Evidence of Expert review

The below specially developed surveys and other study tools are the subject of expert review, which will be recorded in the format of a short report/letter.

Surveys being expertly reviewed for validation:

Participant perspectives surveys:

- Participant perspectives baseline survey (Appendix 4)
- Participant perspectives outcome survey (Appendix 7)

Tools being expertly reviewed for general suitability for use:

- Quality of Life measure (Appendix 5)
- Mobility+ flow rate guide (See LA030 attached to protocol)
- Phone communication check sheets (Trial days – Appendix 6)
- Phone communication check sheets (Study days 7 and 14 - Appendix 8)
- General end of study questions (end of Appendix 7)
- Giving set decision trees (Figures 6 and 7)
